7.7.1 Other concomitant treatment

Other medication other than that described above, which is considered necessary for the subject's safety and well-being, may be given at the discretion of the Investigator and recorded in the appropriate sections of the Case Report Form.

7.8 Post study access to study treatment

Patients receiving AZD9291 at the time of study reaches to final DCO (i.e., after final data cut-off date) may continue to receive AZD9291, if in the opinion of their treating physician they are continuing to derive clinical benefit from continued treatment. Such patients will continue to be monitored and all safety assessments that may be related to IP and drug dispensing/accountability, until AZD9291 is permanently discontinued. For Pregnancy reporting during continued access, see Section 6.6 (Pregnancy). These patients will then be followed up for a period of 30 days after the last AZD9291 dose is administered for any new treatment-related serious adverse events, in accordance with Section 6.4 (Reporting of serious adverse events). All SAEs, overdoses and pregnancies would be reported until 30 days after last dose.

If study drug would be approved on market for use in disease under study indication, patients may be discontinued and switched to market product. Drug supply options can be available depending on the country and would be proposed to patient when found as best way to continue treatment by both AZ and investigator. Study would be open until last patient treated. Final Last Subject Last visit will be defined as last patient's treatment discontinuation.

Data collected for patients who continue to receive AZD9291 after study completion will only be recorded in the source documents; these data will neither be entered into the study database nor reported as an addendum to the CSR.

8. STATISTICAL ANALYSES BY ASTRAZENECA

8.1 Statistical considerations

A comprehensive Statistical Analysis Plan (SAP) will be prepared prior to first subject enrolled. All Analyses will be performed by AstraZeneca or its representatives. Additional details relating to the Independent Central Review will be detailed in the Independent Central Review Charter.

The data cut-off for the primary analysis of ORR will take place 18 weeks after the last subject enrolled, to allow opportunity for all patients to complete two RECIST follow-up assessments. At this time, DoR and safety/tolerability will also be summarised. The primary analysis CSR will report the analysis of ORR supported by duration of response, and safety and tolerability data.

The full CSR will report the analysis of all primary and secondary endpoints (including updated ORR and DoR, DCR, tumour shrinkage, PFS, OS, Safety and HRQoL) and summarise the exploratory endpoint of patient reported adverse events (PRO-CTCAE). The data cut-off for this analysis will take place approximately 12 months after the last subject has been enrolled, to allow responding patients to have a DoR greater than 6 months.

All patients will continue to be followed up in order to capture the reliable overall survival data based on a final data cut-off when approximately 95 OS events (about 55% maturity) have been observed out of all enrolled. The final analyses will include the analysis for OS PRO and Safety data at this DCO. Analysis for RECIST related endpoints (ORR, DoR, tumor shrinkage, DCR and PFS) cut-off at RECIST modules freeze time will be also performed at final analysis.

8.2 Sample size estimate

The study will recruit approximately 175 patients with EGFRm+ and T790M+ mutation positive locally advanced or metastatic NSCLC, whose disease has progressed following either one prior therapy with an EGFR-TKI (chemotherapy-naïve, 33%) or following treatment with both EGFR-TKI and a platinum-based doublet chemotherapy (Patients may have also received additional lines of treatment, 67%). With 175 patients the precision of the estimation of ORR in the overall study population will be within +/-8% (e.g. ORR 40%, 95% CI 33.0%, 47.4%; ORR 50%, 95% CI 42.1%, 57.4%). In Chinese patients subgroup and for ORR 50%, the precision of the estimation of ORR will be within +/-14% in the 50 patient cohort who have only received previous EGFR-TKI treatment and within +/-10% in the 100 patient cohort who have received previous treatment with both an EGFR-TKI and a platinum-

based doublet chemotherapy. The study will also provide an adequate number of patients in which to assess the safety and tolerability of AZD9291; if zero events are observed in the 175 patients, there is 95% confidence that the true event rate is less than 2.2%.

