Patients may continue to receive AZD9291 after disease progression as long as they are continuing to receive clinical benefit, as judged by the investigator, and in the absence of discontinuation criteria (see Section 3.6).

Investigational product, dosage and mode of administration

AZD9291 is an oral, potent, selective, irreversible inhibitor of both EGFR mutation and T790 mutations in NSCLC with a significant selectivity margin over wild-type EGFR. AZD9291 will be administered orally as a 80 mg tablet once a day. A cycle of treatment is defined as 21 days of once daily AZD9291 treatment.

Statistical methods

One primary objective of the study is to assess the efficacy of AZD9291 defined by assessment of best ORR which is defined as the number (%) of patients with measurable disease who had confirmed CR or PR assessed by ICR per RECIST 1.1.

The study was designed to estimate the response rates in patients with EGFRm+ and T790M+ locally advanced or metastatic NSCLC who have progressed on or after first line EGFR-TKI treatment or a line of EGFR-TKI and a line of platinum containing doublet chemotherapy regardless the sequence of treatment. ORR will be estimated with 95% exact CIs. With 175

patients the precision of the estimation of ORR in the overall study population will be within +/-8% (eg, ORR 40%, 95% CI 33.0%, 47.4%, ORR 50%, 95% CI 42.1%, 57.4%). The ORR will also be presented by patient cohort: patients who received previous TKI only; patients who received a TKI and a platinum-based doublet chemotherapy (patients may have also received additional lines of treatment).

Secondary efficacy variables include: DoR, DCR, tumor shrinkage, PFS (according to RECIST 1.1 as assessed by ICR); HRQoL and symptoms; overall survival (OS).

For the primary analysis, ORR will be based on ICR defined visit responses. The imaging scans will be reviewed by two independent radiologists blinded to individual patient data using RECIST 1.1 criteria and will be adjudicated if required. For each patient, the ICR will define the overall visit response data and the relevant scan dates for each time point (ie, for visits where response or progression is/is not identified). Endpoints (ORR, DoR, DCR, PFS) will be derived from the overall visit response data and the scan dates. Sensitivity analyses of ORR, DoR, DCR and PFS from the investigators assessment will also be performed. The concordance between ORR as assessed by ICR and by investigator will be presented.

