1.5 Study design

This is a phase II, open label, single arm study assessing the safety and efficacy of AZD9291 (80 mg, orally, once daily) in patients with a confirmed diagnosis of EGFRm+ and T790M+ locally advanced or metastatic NSCLC (Stage IIIB-IV), who have progressed following prior therapy with an approved EGFR-TKI agent.

In order to enrol approximately 175 patients it is expected that approximately 440 patients will be screened. The 150 patients from China will compose 2 cohorts:

- Approximately 50 patients with EGFRm+ and T790M+ NSCLC who have progressed following 1st line EGFR-TKI treatment but who have not received further treatment
- Approximately 100 patients with EGFRm+ and T790M+ NSCLC who have progressed following prior therapy with an EGFR-TKI and a platinum-based doublet chemotherapy. Patients may have also received additional lines of treatment.

[figure not shown]
The remaining 25 patients are from other countries. It is expected to enroll patients in a similar ratio between the 2 cohorts as that of the Chinese patient group, e.g. approximately 8 patients from 2nd line and 17 patients from 3rd line or beyond. Patients who have prior neo-adjuvant or adjuvant chemotherapy treatment within 6 months of starting 1st EGFR TKI treatment will be treated as 3rd line patients.

The study size has been selected in order to make an accurate assessment of safety/tolerability and to estimate ORR with 95% confidence intervals that are within +/- 8%. The sample size of the Chinese group of each cohort has been selected in order to provide acceptable precision of the estimation of ORR (ORR 50%, +/-11% for multiple therapies; +/-13% for previous TKI only). Enrolment to individual cohorts may be closed separately. Sites will be informed in advance of cohort closure timelines.

A mandatory biopsy will be needed for central testing of T790M mutation status following confirmed disease progression on the most recent treatment regimen. The T790M mutation status of the patient's tumour must be determined by the designated central laboratory using the cobas® EGFR Mutation Test - and/or the ADx-EGFR test.

Patients should continue on treatment with AZD9291 until RECIST 1.1 defined progression or until a treatment discontinuation criterion is met. There is no maximum duration of treatment as patients may continue to receive AZD9291 beyond RECIST 1.1 defined progression as long as they are continuing to show clinical benefit, as judged by the investigator.

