8.7.1 Analysis of the primary variable(s)

Objective response rate (ORR) by ICR in the evaluable for response analysis set will be presented together with 95% exact (Clopper Pearson) confidence intervals. Summaries of the number of patients with best response in each of the follow categories will be summarised: Complete Response (CR), Partial Response (PR), Stable Disease (SD), Progressive Disease (PD) and Non-Evaluable (NE).

The baseline patient characteristics will be summarised, including demographics, EGFR mutation type and prior anti-cancer therapy, including most recent previous treatment.

Additional summaries of ORR will be performed

- ORR by investigator assessment
- ORR summarised for both confirmed and unconfirmed responses
- ORR by EGFR mutation subtype: Exon 19 deletion/L858R/Other.
- ORR in the subgroup of patients who received TKI as last treatment prior to study start and those whose treatment prior to study start was not a TKI
- ORR at week 6 and 12 will also be summarised.

The concordance between ORR as assessed by ICR and by investigator will be presented.

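### Sections 1.5 and 8.2 give different precisions for the same Chinese cohorts, and only one of the four figures holds under the planned exact interval

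*Protocol*

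**What the plan says.** Section 1.5 links the size of the Chinese cohorts to precision: "The sample size of the Chinese group of each cohort has been selected in order to provide acceptable precision of the estimation of ORR". The figures it gives are "ORR 50%, +/-11% for multiple therapies; +/-13% for previous TKI only". The smaller cohort is described as "Approximately 50 patients with EGFRm+ and T790M+ NSCLC who have progressed following 1st line EGFR-TKI treatment but who have not received further treatment"; the larger has about 100 patients who had both an EGFR-TKI and a platinum doublet.

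Section 8.2 returns to the same cohorts at the same rate ("In Chinese patients subgroup and for ORR 50%, the precision of the estimation of ORR will be") and states a different pair: "within +/-14% in the 50 patient cohort who have only received previous EGFR-TKI treatment and within +/-10% in the 100 patient cohort".

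The interval method is fixed. The synopsis says "ORR will be estimated with 95% exact CIs", and Section 8.7.1 says that ORR by independent review "will be presented together with 95% exact (Clopper Pearson) confidence intervals".

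For all 175 patients, the synopsis and Section 8.2 claim a precision within ±8% and give two examples. The first is "ORR 40%, 95% CI 33.0%, 47.4"%; the second is 42.1-57.4% at an ORR of 50%.

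**The concern.** The two pairs describe the same patients at the same assumed rate and should agree. They differ in opposite directions: from Section 1.5 to Section 8.2 the small cohort's figure goes up (13 to 14) and the large cohort's goes down (11 to 10). A single change of method or of sample size would move both the same way, so neither section can simply be a rounding of the other.

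The study sets no hypothesis test or success threshold on ORR, so on the efficacy side the size of each cohort is argued from interval width. The Chinese cohorts make up 150 of the 175 patients and are to be summarised separately (Section 8.7.3). A reader should be able to tell what precision was intended, and the stated figure should come from the interval that will be reported.

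**Working it through.** **Inputs.** n = 50 and n = 100 (Section 1.5); ORR 50% (Sections 1.5 and 8.2); two-sided 95% Clopper-Pearson interval (Section 8.7.1); n = 175 with ORR 40% and 50% (synopsis and Section 8.2).

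**Step 1: reproduce the plan's figures.** The Wald half-width is 1.96 × √(p(1−p)/n).
- n = 50: 1.96 × √(0.25/50) = 13.86 points, which rounds up to within 14.
- n = 100: 1.96 × √(0.25/100) = 9.80 points, which rounds up to within 10.

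This reproduces the Section 8.2 pair. The Section 1.5 pair comes from no single method tried:

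| Method | n = 50 | n = 100 |
|---|---|---|
| Wald | 13.86 | 9.80 |
| Wilson | 13.36 | 9.62 |
| Jeffreys | 13.53 | 9.68 |
| Wald with continuity correction | 14.86 | 10.30 |
| Clopper-Pearson | 14.47 | 10.17 |

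Only Wilson rounds to 13 at n = 50, and no method rounds to 11 at n = 100. Adding the patients from other countries (50 + 8 = 58 and 100 + 17 = 117) does not help: the exact half-widths become 13.4 and 9.4, and the Wald ones 12.9 and 9.1.

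**Step 2: apply the planned method.** The lower limit is the 0.025 quantile of Beta(x, n−x+1), and the upper limit is the 0.975 quantile of Beta(x+1, n−x).
- 25/50: 35.53-64.47%, half-width 14.47 points.
- 50/100: 39.83-60.17%, half-width 10.17 points.

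| Stated | Section | Exact | Shortfall (points) |
|---|---|---|---|
| ±13% (n = 50) | 1.5 | 14.47 | 1.47 |
| ±14% (n = 50) | 8.2 | 14.47 | 0.47 |
| ±10% (n = 100) | 8.2 | 10.17 | 0.17 |
| ±11% (n = 100) | 1.5 | 10.17 | none |

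To give a sense of scale, exact intervals at 50% would need about 62 patients for ±13%, 54 for ±14% and 104 for ±10%.

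**Step 3: the overall examples.**
- 70/175 = 40%: Wilson gives 33.03-47.40%, which is the printed interval. Clopper-Pearson gives 32.68-47.66%.
- 87/175 = 49.7%: Clopper-Pearson gives 42.08-57.36%, which is the printed 50% example. Half of 175 is not a whole number, so this example is sound.
- The largest exact half-width at n = 175 is 7.64 points, and the longest distance from the estimate to either limit is 7.69 points. The overall ±8% holds.

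Section 8.2 therefore contains Wald, Wilson and Clopper-Pearson results, although only the last is planned.

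**The case against.** The strongest reply is that very little turns on this. Exact half-widths of 14.47 and 10.17 round to the 14 and 10 in Section 8.2, the cohort sizes are themselves approximate, and the overall examples are illustrations that differ from the exact limits by about 0.3 points. The exact interval will be computed from the observed data whatever these sections say. Most of this stands, and it settles the grade. It does not remove the conflict between the two sections or the 1.5-point understatement in ±13%. Section 8.2 also words its figures as upper bounds, which the planned interval exceeds even at full enrolment.

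A reader might infer three stronger things that the document does not support.

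- **That precision is the only basis for the sample size.** Section 1.5 also names assessment of safety and tolerability, and Section 8.2 adds a bound on the event rate when no events are seen in 175 patients.
- **That the overall ±8% fails because the primary analysis uses the evaluable-for-response set.** The claim is made for 175 patients and is true for them. Inclusion criterion 9 requires a measurable lesion, so patients drop out of that set only when independent review disagrees at baseline, and the protocol gives no rate for this. The smallest set that keeps ±8% also depends on the measure: 160 by half-width (7.996 points; 159 gives 8.02), or 163 by the longer distance to a limit (7.98 points; 162 gives 8.002). No single threshold should be written into the protocol.
- **That the cohorts are too small.** No required precision is fixed beyond what is called acceptable, so the figures show a misstatement and not under-enrolment.

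**Conclusion.** The point holds as a minor error of statement. Sections 1.5 and 8.2 contradict each other on both Chinese cohorts. Under the planned Clopper-Pearson interval at an ORR of 50%, ±13% is materially too narrow, ±14% and ±10% are slightly too narrow as bounds, and ±11% is true. The 40% example for the whole study comes from a method other than the planned one.

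These results assume exactly 50 and 100 patients, all evaluable for response, and an observed rate of 50%. Any loss from the evaluable set would widen the intervals, by an amount the document does not let one estimate. Type I error, power, enrolment and the intervals eventually reported are unaffected.

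**What to change.** State one pair of exact figures in Sections 1.5 and 8.2: at an ORR of 50%, ±14.5% for n = 50 (35.5-64.5%) and ±10.2% for n = 100 (39.8-60.2%). If a bound is preferred, within ±15% and within ±11% are both true.

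In the synopsis and Section 8.2, replace the 40% example with 32.7-47.7% (70/175). Keep 42.1-57.4%, ideally labelled as 87/175, and keep the overall ±8%. Add one sentence saying that all these figures are Clopper-Pearson and assume that every patient is evaluable for response.

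The cost is protocol wording only. Some stated precisions become slightly less favourable; enrolment and analysis do not change.

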8.3 Definitions of analysis sets

8.3.1 Full analysis set

The full analysis set is defined as all patients enrolled who received at least one dose of investigational product.

Safety data summaries and analyses will be produced based on the full analysis set.

8.3.2 Evaluable for response analysis set

The evaluable for response analysis set will be all patients who have received at least one dose of treatment and have measurable disease at baseline according to the independent review of baseline imaging data.

The primary analysis of ORR, and other RECIST-based outcomes by independent central review will be produced based on the evaluable for response analysis set. All other efficacy variables will be summarised using the full analysis set.

To support the primary analysis, demographic data will also be summarised for the evaluable for response analysis set.

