8.4 Outcome measures for analyses

Independent Central Review of RECIST based assessments

The Independent Central Review of all radiological imaging data will be carried out using RECIST version 1.1. All radiological scans for all patients (including those at unscheduled visits, or outside visit windows) will be provided to the ICR. Prior radiotherapy reports for patients (at baseline) and information on biopsied lesions will also be provided to the ICR to allow the selection of appropriate target lesions. The imaging scans will be reviewed by two independent radiologists using RECIST 1.1 criteria and will be adjudicated if required. For each patient, the ICR will define the overall visit response data (CR, PR, SD, PD or NE) and the relevant scan dates for each time point (ie, for visits where response or progression is/is not identified). If a patient has had a tumour assessment which cannot be evaluated then the patient will be assigned a visit response of not evaluable (NE) (unless there is evidence of progression in which case the response will be assigned as PD). Endpoints (ORR, DoR, DCR, PFS) will be derived from the overall visit response date and the scan dates. ORR will only include patients whose response has been confirmed by a second scan at least 4 weeks after

the initial response. The endpoint of tumour shrinkage will be assessed from tumour size measurements based on the primary independent radiologist assessment.

Further details of the Independent Central Review will be documented in the Independent Review Charter.

Investigator RECIST based assessments

From the investigators review of the imaging scans, the RECIST tumour response data will be used to determine each subject's visit response according to RECIST version 1.1. It will also be used to determine the endpoints ORR, DoR, DCR and PFS from the overall visit response and scan dates.

At each visit, patients will be programmatically assigned a RECIST 1.1 visit response of CR, PR, SD or PD depending on the status of their disease compared with baseline and previous assessments. If a patient has had a tumour assessment which cannot be evaluated then the patient will be assigned a visit response of not evaluable (NE) (unless there is evidence of progression in which case the response will be assigned as PD).

Please refer to [Appendix C](#) for the definitions of CR, PR, SD and PD.

Overall Response Rate (ORR)

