PFS is defined as the time from enrolment until the date of objective disease progression or death (by any cause in the absence of progression) regardless of whether the patient withdraws from study therapy or receives another anti-cancer therapy prior to progression. Patients who have not progressed or died at the time of analysis will be censored at the time of the latest date of assessment from their last evaluable RECIST assessment.

However, if the patient progresses or dies after three or more missed RECIST assessments visits, the patient will be censored at the time of the latest evaluable RECIST assessment. If the patient has no evaluable visits or does not have baseline data they will be censored at 0 days unless they die within two visits of baseline.

The PFS time will always be derived based on scan/assessment dates not visit dates.

RECIST assessments/scans contributing towards a particular visit may be performed on different dates. The following rules will be applied

- Date of progression will be determined based on the earliest of the dates of the component that triggered the progression
- When censoring a patient for PFS the patient will be censored at the latest of the dates contributing to a particular overall visit assessment

Overall Survival

Overall survival is defined as the time from the date of first dose until death due to any cause. Any patient not known to have died at the time of analysis will be censored based on the last recorded date on which the patient was known to be alive.

Note: Patients should be contacted in the 2 weeks following the data cut-off for the final survival analyses to provide complete survival data

HRQoL & Symptoms

Patient reported outcomes will be assessed using the EORTC QLQ-C30 and QLQ LC13 questionnaires. The QLQ-C30 consists of 30 questions which can be combined to produce 5

functional scales (Physical, Role, Cognitive, Emotional, Social), 3 symptom scales (Fatigue, Pain, Nausea/vomiting), 5 individual items (dyspnoea, insomnia, appetite loss, constipation, diarrhoea) and a global measure of health status. The QLQ LC13 is a lung cancer specific module comprising 13 questions to assess lung cancer symptoms (cough, haemoptysis, dyspnoea and site-specific pain), treatment related side-effects (sore mouth, dysphagia, peripheral neuropathy and alopecia) and pain medication. With the exception of a multi-item scale for dyspnoea, all are single items.

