PFS will be displayed using a Kaplan-Meier plot. The number events, median (calculated from the Kaplan Meier plot), and the proportion of patients without an event at 6, 12, 18 and 24 months summarised. PFS will be presented based on the ICR assessments, and as a sensitivity analysis PFS will be presented based on the investigator assessment.

Overall Survival (OS)

When there is sufficient data (>20 events), OS will be displayed using a Kaplan-Meier plot. The number events, median (calculated from the Kaplan Meier plot), and the proportion of patients without an event at 6, 12 and 18 months will be summarised.

As appropriate, summaries of the number and percentage of patients who have died, are still in survival follow-up, are lost to follow-up and have withdrawn consent will be presented.

HRQoL and symptoms

Time to symptom deterioration

For each of the 6 symptoms scales/items in QLQ LC13 (dyspnoea, cough, haemoptysis, chest pain, arm/shoulder pain, other pain) time to deterioration in symptoms will be presented using a Kaplan-Meier plot. Summaries of the number and percentage of subjects experiencing a clinically meaningful deterioration or death, and the median time to deterioration will be also be provided. The proportion of patients alive and free from symptom deterioration at 3, 6, 12 and 24 months will be summarized using the Kaplan-Meier estimates.

Symptom Improvement Rate

For each of the symptom scales/items in QLQ LC13, a 95% confidence interval for symptom improvement rate will be constructed using the Newcombe-Wilson method. In addition, the change from baseline at each assessment time point (in terms of proportion of patients improved, stable, and worsened as defined in Section 8.4) and the mean change from baseline scores at each time point will be summarised for all symptom scales/items from the QLQ LC13 and QLQ-C30.

Definition of clinically meaningful changes

For each functional scale in the QLQ-C30 (physical, role, emotional, cognitive, social) and for Global Health status, the change from baseline at each assessment time point (in terms of proportion of patients improved, stable, and worsened as defined in Section 8.4) and the mean change from baseline scores at each time point will be summarised.

Safety Assessments

Safety and tolerability data will be presented using summaries and descriptive statistics, as detailed in the SAP.

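### Section 8.3.2 puts ICR-assessed PFS on the evaluable-for-response set, which does not fit the PFS definition and, read literally, separates it from investigator PFS and OS

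*Protocol*

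**What the plan says.** Section 8.3.1 sets the broad population: "The full analysis set is defined as all patients enrolled who received at least one dose of investigational product". Section 8.3.2 sets the narrower one, for dosed patients who "have measurable disease at baseline according to the independent review of baseline imaging data". It then allocates endpoints in two sentences. The first is "The primary analysis of ORR, and other RECIST-based outcomes by independent central review will be produced based on the evaluable for response analysis set". The second is "All other efficacy variables will be summarised using the full analysis set".

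PFS is one of the ICR outcomes. In its paragraph on the ICR, section 8.4 says "Endpoints (ORR, DoR, DCR, PFS) will be derived from the overall visit response date and the scan dates". Section 8.7.2 gives the two assessors their roles: "PFS will be presented based on the ICR assessments, and as a sensitivity analysis PFS will be presented based on the investigator assessment".

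The PFS definition in section 8.4 sets no condition on measurable disease: "PFS is defined as the time from enrolment until the date of objective disease progression or death (by any cause in the absence of progression". Its censoring rule adds "If the patient has no evaluable visits or does not have baseline data they will be censored at 0 days", with an exception for death within two visits of baseline.

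**The concern.** Measurable disease at baseline is needed to score an objective response. It is not needed to observe progression through new or non-target lesions, or to observe death. A rule that suits ORR has been extended to PFS by a general phrase.

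Three things are at stake. The ICR PFS estimate would not describe all treated patients, because some would leave it on the strength of a central reading of the baseline scan, and their deaths would leave with them. Investigator PFS is meant to show how far the result depends on who reads the scans, and that comparison is less clean if the population changes as well. PFS and OS would also be reported for slightly different patients.

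**Working it through.** **Which set each analysis falls in**

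| Analysis | Set | Basis |
|---|---|---|
| ICR ORR, DCR, DoR | Evaluable for response | 8.3.2, first sentence; 8.4 list |
| ICR PFS | Evaluable for response | 8.3.2, first sentence; PFS is in the 8.4 list |
| Investigator PFS | Full analysis set | Inferred from 8.3.2, second sentence; not named |
| OS | Full analysis set | 8.3.2, second sentence |

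Nothing later overrides this. Section 8.7 refers to the two sets as appropriate. The PFS paragraph of 8.7.2 and section 8.7.5 name no set. By contrast, 8.7.1 and 8.7.2 name the evaluable set for ORR and DCR.

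**Does the set fit the PFS definition?**

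- Section 8.4 restricts ORR to patients with measurable disease and puts no such restriction on PFS.
- Appendix C, written for the investigator's use of RECIST 1.1, allows visit responses when there are no target lesions (Table 13). It counts non-target progression or a new lesion as progression.
- The censoring rule has two limbs. The limb on no evaluable visits can apply inside the evaluable set. The limb on missing baseline data cannot, because a patient without baseline imaging cannot have been read as having measurable disease. For ICR PFS on that set, the second limb has nobody to act on.

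**Can a treated patient be excluded?** Yes. Inclusion criterion 9 requires a measurable lesion, but no ICR confirmation before enrolment is stated. Section 5.1.2 says ICR results are not passed to investigators. Under 8.4 the ICR selects its own target lesions, using radiotherapy and biopsy information.

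**Size**

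The protocol gives no PFS assumption and no expected number of exclusions, so there is no PFS figure to reproduce. Its ORR precision example at 50% does reproduce (87/175, exact 95% CI 42.1% to 57.4%), but this point does not bear on it. The only input from the protocol below is N = 175.

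The assumptions are an excluded share e of 2% to 15%, exponential PFS with a median of 10 months in evaluable patients, and a median m of 4, 7 or 14 months in excluded patients. PFS in the full set is then

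S(t) = (1 − e) × 0.5^(t/10) + e × 0.5^(t/m),

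and its median solves S(t) = 0.5.

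| e | Excluded / kept | Full-set median, m = 4 | m = 7 | m = 14 | Full-set 12-month PFS, m = 4 to 14 |
|---|---|---|---|---|---|
| 2% | 4 / 171 | 9.81 | 9.93 | 10.06 | 42.9% to 43.8% |
| 5% | 9 / 166 | 9.54 | 9.82 | 10.16 | 42.0% to 44.1% |
| 10% | 18 / 157 | 9.09 | 9.64 | 10.32 | 40.4% to 44.7% |
| 15% | 26 / 149 | 8.66 | 9.46 | 10.49 | 38.9% to 45.3% |

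The evaluable-set values are 10.0 months and 43.5%. Across the grid, the full-set median lies between 1.34 months below and 0.49 months above the evaluable-set median. For e of 5% to 10%, the range is 0.91 below to 0.32 above.

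The loss of precision is about 1/√(1 − e): 1.026 at 5% and 1.054 at 10%, so the standard error rises by 3% to 5%.

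For scale, with an assumed 100 exponential PFS events, a 95% interval around a 10-month median is about 10 × exp(±1.96/√100), or 8.2 to 12.2 months.

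**The case against.** The strongest reply is that the PFS population is not really settled. Section 8.3.2 does not mention PFS by name, 8.7 leaves the choice of set open, the PFS paragraph names none, and the censoring rule already points to all treated patients. On that view this is drafting that a statistical analysis plan would settle. Part of this stands: the protocol pulls both ways. But 8.3.2 is a stated allocation that covers PFS through the list in 8.4, so it needs correcting rather than filling in.

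The reply is also right on these points:

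- **Investigator PFS.** That it uses the full analysis set is an inference from the residual sentence in 8.3.2. The like-for-like complaint depends on that reading.
- **Direction.** A reader might infer that excluded patients have less tumour, so that ICR PFS is biased downwards. The documents do not support this. Appendix C classes leptomeningeal disease, effusions, bone lesions, brain metastases and previously irradiated lesions as non-measurable, and none of these implies low burden.
- **Attribution.** A reader might infer that no difference between the two PFS results could be put down to the assessor. That is too strong, since only a few patients are likely to differ between the sets.
- **Consequence.** PFS is a secondary, descriptive summary in a single-arm study. Criterion 9 requires a measurable lesion and section 3 allows no exceptions, so only disagreement between centre and site, or unreadable scans, would remove patients. The primary ORR analysis is not affected.

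**Conclusion.** The point holds as a mismatch between sections 8.3.2 and 8.4. A population built for response is applied to an endpoint defined without that condition, and one limb of the PFS censoring rule is left with no one to apply to. On the literal reading, the investigator sensitivity analysis also changes population, and ICR PFS leaves out some treated patients and their deaths.

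The effect is probably small. Under the assumptions shown, the median moves by a few tenths of a month in most scenarios and by at most about 1.3 months, which needs 15% excluded with a much poorer outlook. The sign depends on the prognosis of the excluded patients, which the protocol does not give. This should be corrected because the rule is wrong for the endpoint and cheap to change, not because a large bias has been shown.

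**What to change.** In section 8.3.2, limit the evaluable-for-response set to the ICR response measures (ORR, DCR, DoR and tumour shrinkage). State that PFS by ICR and PFS by investigator are both analysed in the full analysis set. Carry the same wording into the PFS paragraph of 8.7.2, and into the statistical analysis plan if it repeats the rule.

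The cost is a change of text. No new data are needed, because sections 5.1.2 and 8.4 already send the scans of all patients to the ICR. The primary analysis and sample size do not change.

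The drawback is that a few patients without ICR target lesions would contribute PFS based on non-target lesions, new lesions or death. PFS in the evaluable set can be kept as a supportive summary so that readers can see whether this matters.
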